This document is a protocol for a human research study. This study is to be conducted according to US and international standards of Good Clinical Practice (International Conference on Harmonization ICHE6), the Code of Federal Regulations Title 21 parts 803 and 812, and other applicable government regulations.

1.1 *Background*

Annually, over 1 million patients are hospitalized with a primary diagnosis of heart failure (HF)¹. Despite improvement in outcomes with medical therapy, readmissions for acute decompensated HF are common and place a significant burden on the healthcare system. Therefore, strategies for outpatient monitoring and fluid management are needed to reduce HF hospitalizations. Rather than low cardiac output, the main reasons for rehospitalization are symptoms associated with pulmonary and systemic venous congestion due to elevated ventricular filling (end-diastolic) pressures². Remote monitoring of these pressure changes in addition to its surrogate measures, such as intrathoracic impedance, lung fluid levels, systolic time intervals, or the presence of abnormal heart sounds, may help to prevent hospitalization by detecting early evidence of HF decompensation^{3, 4, 5}. In addition, remote monitoring may lead to better access to care and coordination of services.

Given the anticipated importance of remote HF monitoring and fluid management, ZOLL has developed a novel radiofrequency (RF) based heart failure and arrhythmia management system (μ Cor Heart Failure and Arrhythmia Management System). Using the RF data, μ Cor provides an estimate of the thoracic fluid index (TFI). To calculate TFI, the thoracic fluid baseline is determined, and the normalized value is presented as TFI. In conjunction with standard clinical practice for patients with fluid balance issues, the direction of change of TFI over time may provide clinically useful information. In addition to TFI, the system records the electrocardiogram (ECG) through adhesive electrodes and respiration rate, activity, and posture through a tri-axial accelerometer. The purpose of this study is to assess investigator engagement of μ Cor system data in the context of heart failure management.

1.2 *Preclinical Data*

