2.2 Secondary Objective(s)

The specific secondary objectives that will be evaluated during the entire study include:

2.2.1 To identify correlations between μ Cor measurements (physiologic variables including thoracic impedance, cardiac rhythm, respiration rate) and heart failure related clinical events. A heart failure related clinical event is defined in section 6.1.3.

2.2.2 To identify correlations between μ Cor measurements (physiologic variables including thoracic impedance, cardiac rhythm, respiration rate) and patient reported symptoms.

2.2.3 To identify the hospital readmission rate, physician visit rate, and outpatient clinic visit rate of subjects during the study period.

2.2.4 To identify the mortality rate, cause of death, quality of life (QoL), and health care utilization among patients six months and one year after enrollment into the study.

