Unplanned visits to the physician office or hospital will be captured and defined as visits that the subject did not plan beyond 48 hours. In case of adverse skin reaction to the μ Cor adhesive and/or electrodes, on the discretion of physician, subjects may discontinue wearing the device for up to 48 hours. In the event the subject has stopped wearing the device completely, follow up phone calls will continue to be conducted per protocol in order to capture clinical information.

During the Day 90 visit, the subject will be given the option to continue wearing the μ Cor for an additional 90 days. Furthermore, if the subject experienced a heart failure related clinical event within the initial 90 days of wear, the subject will be given the option of wearing the μ Cor for 30 days following the heart failure event. If the subject chooses additional wear time, weekly phone calls and monthly visits will be structured identical to that of the main study period. The μ Cor will be returned at end of use.

Data updates will be delivered to the site when the day averaged TFI exceeds a threshold greater than three standard deviations of the baseline TFI level for three consecutive days. Upon receiving a device data update, the investigator will receive detailed information into how the device measurements have tracked over the days leading up to the notification. When receiving a data update, the site will be required to review the most recent report within 24 hours, and explain their reasoning whether they choose to contact the subject or not to contact the subject. The data review must occur prior to every scheduled subject contact.

When acting upon the data update, the site may contact the subject to assess the subject's current symptoms and history, and make an informed decision within the context of both device measurements and standard medical care as to what actions to take with the subject. Potential actions the site could take will include, a prescription drug change or titration, a request for an office visit, a request for hospitalization, and request for lifestyle or diet modifications. The site will document any changes to subject care within the case report forms. Unscheduled contacts that the subject initiates will be recorded as well.

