8.4 Statistical Methods

Concerning the primary endpoint, investigator engagement will be assessed through the number of data updates delivered by the µCor subject management system, frequency of medication changes based on µCor data, frequency of lifestyle modifications that are recommended to the subject, frequency of medication changes based on symptoms reported by subjects or from subject incidental findings, and frequency high µCor measurements that are reduced below threshold levels after medication was titrated or lifestyle modifications were recommended.

Concerning the secondary endpoints, associations between µCor measurements and clinically related heart failure events will be assessed through sensitivity/specificity analyses. µCor measurements at both baseline (first day of fitting) and the time of heart failure admission will be compared among subjects with or without heart failure related events using t-tests or other appropriate statistical methods.

For primary, secondary, and safety endpoints, descriptive statistics and qualitative analysis will be performed as appropriate. Descriptive statistics will include frequency of data updates delivered by the µCor data system, frequency of physician action to µCor data or µCor data updates, and physician action events as a percentage of all data updates received.

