8.5 Additional Statistical Analysis

NA

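### Section 8.4 specifies no change-from-own-baseline or baseline-adjusted comparison, so for measurements not normalised to the subject an admission-level difference cannot separate a standing difference from a change at the event

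*Combined protocol and SAP*

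**What the plan says.** Objective 2.2.1 is "To identify correlations between μ Cor measurements (physiologic variables including thoracic impedance, cardiac rhythm, respiration rate) and heart failure related clinical events". Section 8.3.2.1 restates it as strength of association. Section 8.4 names two analyses for it:

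- Associations with "clinically related heart failure events will be assessed through sensitivity/specificity analyses". That section gives no cut-off, time window or unit of analysis.
- A comparison of levels at two points, the day the device is fitted and a later one: "the time of heart failure admission will be compared among subjects with or without heart failure related events using t-tests". The sentence ends by leaving room for any other suitable method.

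The contrast named in the second item is between groups of subjects. Section 8.4 mentions no change score, paired analysis, baseline covariate or repeated-measures model, and Section 8.5, on additional analysis, is marked not applicable.

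Two other places bear on the point. Section 1.1 describes the thoracic fluid index (TFI) as a value normalised to a thoracic fluid baseline and says that "the direction of change of TFI over time may provide clinically useful information". The data-update rule in Section 3.1.1 fires when day-averaged TFI "exceeds a threshold greater than three standard deviations of the baseline TFI level for three consecutive days". No comparable normalisation is described for respiration rate, heart rate or activity, which the sensor also records (Section 1.4.1).

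**The concern.** Each subject can supply a first-day value and a later value, so the data carry within-subject information that the named comparison does not use. The two groups are formed by outcome and not by randomisation. Subjects who go on to have an event may well have had a higher respiration rate or heart rate from the first day.

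A level difference at admission then mixes two things: subjects who run higher all the time, and subjects whose value rose with the event. The first describes baseline risk. The second is what a monitor is meant to show. Setting a baseline t-test next to an admission t-test does not separate them, because one significant result and one non-significant result do not amount to a test of change.

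At stake is a statement in the study report that a measurement moves with heart failure events when it may not have moved at all.

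**Working it through.** **Plan's own figure.** There is none to reproduce. Section 8.1 gives 300 subjects at 80 sites as a judgement. The documents state no alpha, power, effect size, event rate or within-subject correlation for this analysis.

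**Inputs.** From the documents: N = 300. Assumed: two-sided 5%; 25% of subjects with an event (75 against 225); equal SD at both times, set to 1; baseline-to-later correlation rho = 0.5; standing gap 0.3 SD; no change at the event; a later value available for event-free subjects.

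**1. Level t-test at admission.** Noncentrality = gap × sqrt(n1·n2/(n1+n2)) = 0.3 × sqrt(75 × 225/300) = 0.3 × 7.5 = 2.25. On 298 degrees of freedom this is significant in about 61% of trials.

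| Standing gap | Event : event-free | Significant at admission |
|---|---|---|
| 0.2 SD | 75 : 225 | 32% |
| 0.3 SD | 75 : 225 | 61% |
| 0.4 SD | 75 : 225 | 85% |
| 0.3 SD | 30 : 270 | 34% |
| 0.3 SD | 120 : 180 | 72% |

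**2. Taking the planned baseline comparison into account.** A standing gap is equally visible on the first day, so the baseline t-test is also significant in about 61% of trials. By simulation at 0.3 SD, the pattern of significant at admission but not at baseline occurs in about 16% of trials at rho 0.5, about 19% at rho 0.3 and 12% to 13% at rho 0.7. At 0.4 SD and rho 0.5 it is 9% to 10%. In the base case, then, 61% − 16% = 45% of trials show the gap at both times.

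**3. Change from own first-day value.** The standing gap cancels in the difference. Simulated rejection is about 5% at every gap and correlation tried.

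**4. Later value with the first-day value as covariate.** The gap left after adjustment is 0.3 × (1 − rho), with residual SD sqrt(1 − rho²). At rho 0.5 this is 0.15/0.866 = 0.173 SD, so the noncentrality is 0.173 × 7.5 = 1.30 and rejection is about 25%. At a gap of 0.4 SD it is about 39%.

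**5. Power when there is a real change and no standing gap.** Take 0.375 SD, which the level t-test detects with 80% power (0.375 × 7.5 = 2.81). The change score uses 0.375/sqrt(2(1 − rho)); the adjusted analysis uses 0.375/sqrt(1 − rho²).

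| rho | Level | Change score | Adjusted |
|---|---|---|---|
| 0.3 | 80% | 66% | 84% |
| 0.5 | 80% | 80% | 90% |
| 0.7 | 80% | 95% | 97.5% |

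No single method has both the 5% error rate and the 90% power. The first belongs to the change score and the second to the adjusted analysis.

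**The case against.** The other side has several good arguments.

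- *The method is left open.* A reader might infer that Section 8.4 commits to two separate t-tests and rules out a within-subject analysis. It does not: the sentence allows other appropriate methods. A change analysis is unspecified, not excluded. What stands is that a method picked once the data are in hand is not prespecified, and the one method named does not address change.
- *A standing difference is still an association.* Objective 2.2.1 and Section 8.3.2.1 ask for correlation or strength of association, and the two passages on following a subject over time concern TFI. A reader might therefore call the 61% a false-positive rate for the endpoint. That goes too far. It is the rate at which a level difference appears without any change, and it misleads only if read as evidence of change.
- *The baseline comparison would often expose the gap.* It would, which is why 16% describes the misleading pattern better than 61%. But the plan has no rule for using the baseline result.
- *TFI is already normalised.* This is accepted, provided that its baseline is the subject's own. The point is confined to the other measurements.
- *A change score has its own weakness.* Day 0 falls at discharge or within 10 days of it, so the first-day value may not be a stable level. If event subjects start 0.3 SD higher and that gap has closed by the later reading, the change test at rho 0.5 also rejects in about 61% of trials (change SD = sqrt(2 × 0.5) = 1, so the noncentrality is again 2.25). This stands and has to be reported as a limitation.

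**Conclusion.** The concern holds as an under-specification. For respiration rate, heart rate and activity, the comparison named in Section 8.4 cannot tell a standing difference from a change at the event, and no other analysis in the plan is specified to do so. How often this matters depends wholly on assumed values. With 75 against 225 subjects, a 0.3 SD gap and rho 0.5, the admission test is significant in about 61% of trials with no change, and the admission-only pattern appears in about 16%.

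The documents do not support reading this as a threat to the study's conclusions. The endpoint is secondary and exploratory, it has no stated alpha or success rule, sensitivity/specificity analyses are named beside the comparison, and the primary endpoint is investigator engagement.

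**What to change.** In Section 8.4:

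1. Keep the level comparisons at the first day and at admission, labelled as descriptive.
2. For measurements not normalised to the subject's own baseline (respiration rate, heart rate, activity), add a comparison of change from the subject's own first-day value, event against event-free subjects.
3. Report beside it the same comparison of later values with the first-day value as a covariate.
4. State that any claim that a measurement changes with an event rests on the change comparison.

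One step must come first. Event-free subjects have no admission, so they need a defined reference day, for example one matched on days since fitting. The same definition should cover events under Section 6.1.3 that are not admissions.

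The cost is wording and analysis work; the device already records these measurements, so no visits or subjects are added. The downsides should be stated in the plan:

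- Subjects without a usable first-day value drop out, since Section 8.6.3 allows no replacement of missing data.
- The change score gains no power over the level test at rho 0.5 and loses power below that.
- The adjusted analysis is more powerful but does not fully remove a standing gap.
- A first-day value taken soon after discharge may not represent the subject's usual level.

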3.1 General Design

3.1.1 Study Description

Subjects meeting the inclusion/exclusion criteria will wear μ Cor for up to 90 days from the day of fitting. 300 total patients will be enrolled. Subjects will be fitted with μ Cor during discharge of a heart failure related hospitalization or within a clinic visit that has occurred within 10 days of a heart failure related hospitalization. The μ Cor fitting will mark day 0 of the study. An LVEF measurement will be recorded during enrollment or within 30 days post enrollment if an LVEF measurement has not been recorded within 30 days prior to enrollment. Any LVEF will qualify for the study. An investigator assessment will be performed during all clinic visits. The assessment template is shown in Appendix A.

Subjects will be given a diary at enrollment that will ask them to rate their degree of specific symptoms of heart failure such as shortness of breath and fatigue as well as mark any heart failure related clinical events or medication changes that have occurred since the last entry. The subject diary is shown in Appendix A.

Phone calls will be based on weekly data reviews or data updates. A review of the data will be conducted by the site before the weekly phone call and the most recent (Transthoracic Fluid Index) TFI will be recorded. The subject will receive a study based weekly phone call asking the subject about any recent heart failure related clinical events or change in heart failure symptoms. The weekly phone calls will continue if the subject has stopped wearing the device. During the weekly phone call the subject will be reminded to fill out the daily diary. No phone calls will be given on the week where there is a study follow up visit.

A review of the data will be conducted by the site before the office visit and the most recent TFI will be recorded. Study face to face follow up visits will occur at day 30, day 60, and day 90. There will be no follow up visit if the subject has stopped wearing the device. During follow up visits the subjects will be asked about any heart failure related clinical events or change in symptoms that have occurred since the last follow up.

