5.4 Early Withdrawal of Subjects

5.4.1 When and How to Withdraw Subjects

All patients enrolled into the study can withdraw at any time regardless of the reason for withdrawal. Patients may withdraw consent for use of data and exit the study at any time without prejudice to further treatment.

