 - Any physician visits, both planned and unplanned
 - Any hospitalization, including heart failure hospitalization
 - Any emergency room visits
 - Any symptoms, including syncope, dyspnea, palpitations and chest pain
- 6.2.4.4 A weight measurement will be obtained.
- 6.2.4.5 Subjects will be given a physical assessment
- 6.2.2.6 Daily cardiac medications taken by the subject will be reviewed and compared to the last listed cardiac medications documented by the study. Any new cardiac medications or changes in medication will be recorded (i.e. dosage changes or new medications administered)
- 6.2.4.7 Subjects will be asked if they would like to continue wear for an additional 90 days. If the subject had experienced a heart failure related clinical event within the previous 90 days, the subject will also be given the option to continue wear for 30 days following the most recent heart failure event.

6.3 *Unscheduled Visits*

- 6.3.1 Clinic visits, ED visits, and hospitalizations that have resulted from a device data update will be defined as unscheduled events. Separately, all heart failure related contact with the subject either initiated by the subject or the site will be defined as an unscheduled visit. Heart failure contact includes, but is not limited to, contact with the subject concerning new or worsening heart failure symptoms such as dyspnea, pedal edema, and shortness of breath.
- 6.3.2 Upon receiving a data update, which will be initiated when the day averaged TFI readings have exceeded for three consecutive days a threshold defined by three standard deviations of baseline TFI, the site study team will reach out to the subject within 24 hours. The data update will be delivered to the site via either fax, email, or phone call.
- 6.3.3 The investigator will make a decision whether to contact the subject or take no further action based on the data update, and document the reason. There will be a structured interview between the investigator and subject. The investigator will have access to a report that displays the device data.
- 6.3.4 If the subject is called after device data update, the subject's symptoms and recent history will be documented, and a medical decision, within the context of standard of care,

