8.6.1 Sources of Missing Data

- 8.6.1.1 Medical records not available
- 8.6.1.2 Subjects who are lost to follow up
- 8.6.1.3 Device error
- 8.6.1.4 Missed phone calls
- 8.6.1.5 Missed visits

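### Section 8.4 compares baseline device measurements between subjects with and without heart failure events by t-test, with no event window and no allowance for incomplete follow-up

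*Combined protocol and SAP*

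**What the plan says.** Section 8.4 gives two analyses for the association between device measurements and events. The first is that associations with "clinically related heart failure events will be assessed through sensitivity/specificity analyses". The second takes "measurements at both baseline (first day of fitting) and the time of heart failure admission" and says they "will be compared among subjects with or without heart failure related events using t-tests or other appropriate statistical methods". The grouping has no event window, censoring rule or person-time. Section 8.5 adds no analysis, and the only handling rule in 8.6.3 is that missing values are not replaced.

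Several places bear on how long a subject is observed:
- **Wear.** The device is worn "for up to 90 days from the day of fitting" (3.1.1). At day 90, "Subjects will be asked if they would like to continue wear for an additional 90 days" (6.2.4).
- **Event capture.** Weekly calls go on after wear stops (3.1.1). A call and chart review at six months and one year cover heart failure events for all subjects (6.4).
- **Early ending.** "All patients enrolled into the study can withdraw at any time regardless of the reason for withdrawal" (5.4.1). The expected sources of missing data include "Subjects who are lost to follow up" (8.6.1), along with missed calls and visits.
- **Calendar.** Enrolment is expected to take 2 years within a 2.5-year study (3.1.2).

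**The concern.** With no window and no censoring, a subject lost at day 20 and a subject event-free for a year both fall in the no-event group. Some subjects counted as event-free were simply not watched long enough, so the grouping mixes event risk with observation time.

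Section 2.2 says the secondary objectives are evaluated during the entire study. Section 8.4 could therefore mean 90 days, wear time, six months or one year, and each choice gives a different event group. At stake is one of the two analyses serving secondary objective 2.2.1. Misclassification weakens a real association. If subjects with worse first-day readings also tend to leave early, the comparison of means can show a difference where there is none, or cancel one that exists.

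**Working it through.** **Inputs from the documents.** 300 subjects at 80 sites (8.1); wear up to 90 days plus an optional 90 (3.1.1, 6.2.4); event follow-up to one year (6.4); 2 years' enrolment in 2.5 years (3.1.2).

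**Not given, so assumed.** 90-day event risk r = 25%, with 15% and 35% as a range; two-sided 5% level; dropout and extension proportions; strength of any link between follow-up length and the measurement.

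The plan has no figure to reproduce for this comparison. Section 8.1 justifies 300 subjects by site engagement (300/80 = 3.75 per site, within its stated three to five), with no effect size, SD, error rate or power.

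**Step 1: calendar.** One-year follow-up inside 30 months needs enrolment by month 30 − 12 = 18. If accrual is even and the 2.5 years is binding, (24 − 18)/24 = 25% of subjects, or 75 of 300, cannot reach one year. The last subjects have about six months.

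**Step 2: chance of entering the event group.** With a constant hazard, P(event by day t) = 1 − (1 − r)^(t/90). For r = 25% at day 180, this is 1 − 0.75² = 44%.

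| r by day 90 | 30 days | 90 days | 180 days | 365 days |
|---|---|---|---|---|
| 15% | 5% | 15% | 28% | 48% |
| 25% | 9% | 25% | 44% | 69% |
| 35% | 13% | 35% | 58% | 83% |

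At r = 25%, if 20% (60 of 300) are lost at day 30, then 25% − 9% = 16% of them, about 10 subjects, would have had an event by day 90 but are counted as event-free.

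**Step 3: effect on the test.** Simulation with N = 300, a standard normal baseline measurement, exponential event times, r = 25%, and 3,000 to 4,000 trials per scenario. The ever/never t-test is set against a Cox score test. The link is the factor by which each SD multiplies the odds of shorter follow-up. Power is at a hazard ratio of 1.3 per SD; in the linked rows, higher values both raise the hazard and shorten follow-up.

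| Follow-up | Link | False positives: t-test / Cox | Power: t-test / Cox |
|---|---|---|---|
| Wear time: 30/90/180 days in 20/50/30% | none | 4–5% / 5% | 62% / 66% |
| same | 1.65 | 21–22% / 5% | 18% / 64% |
| same | 2.0 | 36–37% / 5% | 9% / 63% |
| 90-day window, 20% lost at day 30 | 1.65 | 7% / 5% | 32% / 54% |
| same | 2.0 | 10% / 5% | 26% / 54% |
| One year, 15% lost at day 60 | none | – | 85% / 94% |

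**Step 4: a different form of link.** Here follow-up and measurement are correlated through a latent normal variable, and ranges run over r = 15% to 35%. For follow-up taken as wear time, t-test false positives are 10% to 16% at |ρ| = 0.2 and 23% to 49% at ρ = −0.4. For one-year capture with 15% attrition they are 6% to 11% and 12% to 31%. With no link in the wear-time case they are 4.6% to 5.1%. With complete follow-up in a fixed 90-day window they are 4.5% to 5.8%. Cox gives 4.4% to 5.9% throughout.

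**The case against.** A reader might infer that follow-up varies widely by design and that the t-test therefore mainly compares long with short observation. The documents do not support that. The 90-versus-180-day split is device wear, not event capture: calls continue after wear stops, all subjects have a call and chart review at six months and one year, and 5.4.2 asks for follow-up data on withdrawn subjects without contacting them. The 21% to 37% figures belong to the wear-time reading only.

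Nor does unequal follow-up by itself produce a false association: without a link to the measurement the error rate stays near 5%. The link strengths and dropout mixes are assumptions. A calendar cut-off has no evident reason to be related to a first-day reading.

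Section 8.4 also leaves other methods open, names sensitivity and specificity first, and sets no error rate for this secondary comparison. Objective 2.2.1 does not rest on the t-test alone. All of this stands.

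It can further be argued that stating a window does most of the repair. For false positives that is largely right: in a 90-day window with 10% lost at day 30 they are only 6% to 7%. It is less right for power, where with 20% lost at day 30 the linked scenarios give 32% and 26% for the t-test against 54% for Cox. Permission to use another method is also not a commitment to one; it leaves window and method to be chosen after the data are seen.

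One caution about Cox stands. In these simulations loss depends only on the measurement in the model, which is the case most favourable to Cox. Where loss depends on unmeasured severity, 5% has not been shown.

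**Conclusion.** The point holds in a limited form. Section 8.4 groups subjects by event status with no window and no allowance for incomplete follow-up, although the plan itself expects withdrawal and loss and its calendar may cut off late enrollees. Misclassification and some loss of power follow, for example 85% against 94% with one-year capture, 15% lost at day 60 and no link.

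Bias in either direction is conditional on follow-up length being related to the measurement. That is plausible, since sicker subjects may die or withdraw sooner, but it is not shown. With no dropout, extension or event rates in the documents, its actual size is unknown. On the assumed inputs, false positives are about 7% to 10% in a 90-day window with 20% early loss, and reach 21% to 37% only if events are counted over wear time. The primary endpoint is unaffected. The change is worth making because it is cheap and serves a named secondary objective.

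**What to change.** In 8.4, state one event window, for example the first 90 days from start of wear. For the baseline measurement, make the main analysis a Cox model for time from start of wear to first heart failure event, with the measurement per SD as covariate and censoring at last contact or end of window. State how death is handled. Keep the group means as a descriptive table.

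The cost is a few sentences of analysis wording. Calls, visits, diary and chart review already capture events; the sponsor should confirm that the case report forms record the date of each event and of last contact. The downside is a hazard ratio instead of a simple difference in means. This change does not address the admission-time comparison in the same sentence, where subjects without an event have no corresponding time point.
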